#### 18.1.3. Bias

Reporting bias may occur if participants view heat exposure as a nuisance, rather than a health hazard, and under-report clinically-relevant symptoms. To minimise this bias, we will sensitise the communities and begin all activities by giving some background about heathealth risk

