Ultimately, we aim to test the Interventional Framework, described in Figure 2, in the HAPI study [59], focusing on the third trimester of pregnancy and childbirth when biological and socio-economic vulnerabilities are highest [30, 59]. The eventual package of interventions will be *multi-level* (individual-, household-, community-, facility-, and policy-level), and *multi-component*, encompassing behaviour change and awareness, health services, built environment and nature- based interventions, together with activities to facilitate policy shifts. Examples of possible interventions are presented in Appendix 01.

The presence of robust MNH platforms, together with evidence from the HAPI study, will be instrumental in convincing climate financers such as the Green Climate Fund [57] that heathealth interventions in LMICs are feasible and require urgent scaled-up financing.

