### 11. QUASI-EXPERIMENTAL PRE-POST INTERVENTION STUDY.

We apply a quasi-experimental pre-post-intervention design to evaluate intervention feasibility, processes, scalability, pilot-effectiveness, and health and social outcomes. In Zimbabwe, 400 women attending antenatal clinics at weeks 26-30 weeks of gestation will be enrolled before and then during intervention (named 'post-intervention cohort') (total n=800), and assessed four-weekly during pregnancy at routine clinic visits, and subsequently at childbirth and postpartum (planned within 72 hours). Semi-structured questionnaires will be administered to collect data on socio-economic status, heat impacts, behaviours related to heat and hydration, access to safe water, heat-resistance of dwellings, indigenous coping strategies, preferences around intervention attributes, intervention rankings, critical uncertainties, costs of service access and intervention participation, and implementation challenges (See appendix 31) We will also conduct biomedical assessments (ultrasound, blood and urine samples), and screening of wellbeing and for mental health conditions. Additional data will be extracted from the patient-held antenatal cards and birth records. Outcomes in the pre-intervention cohort of women will be compared with women in the post-intervention cohort.

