#### 11.1.9. Data collection

Data collection will occur at enrolment (26-30 weeks), and at a 4-week antenatal care follow-up visit visit , at childbirth and within 72 hours postpartum. These visits coincide with the MoHCC Basic Antenatal Care Visit Schedule for pregnant women . Informed consent will be conducted on the day of enrolment, following procedures described above and in further detail in Section 31. Contact details including telephone numbers, alternate telephone numbers and home address will be collected and logged separately from the database that captures study information

The first interview will take place during the summer months (between November 2024 - February 2025) with follow-up interviews conducted over the remainder of the hotter season, as per the schedule below(figure 9). Ideally pre-intervention cohort visits will be conducted from November 2024 to May 2025 and post-intervention cohort visits will be conducted from November 2025 to May 2026.

All interviews will be carried out by a research staff member and HCWs trained in conducting interviews and collecting study biomarkers. Enrolment semi-structured questionnaires will be interviewer-administered via CAPI (computer assisted personal interviewing) using a study tablet computer to collect data variables such as demographics, socioeconomics, housing type, water and electricity access, heat-related knowledge, current impacts of heat, behaviors related to heat and hydration, housing characteristics, and knowledge and use of indigenous coping strategies. Follow-up visit interviewer-administered questionnaires will be shorter and focus on heat-related knowledge, current impacts of heat, behaviors related to heat and hydration, use of indigenous coping strategies, access to safe water with post-intervention

postpartum questionnaires also including questions on preferences around intervention attributes, intervention rankings, critical uncertainties, costs of service access and intervention participation, implementation challenges, and reflections on the process of participating in this study. Questionnaires and interviews will be conducted in the language of participants' choice (but restricted to languages spoken fluently by the interviewers in our team).

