## 12.1.2. Intervention implementation through action research

A set of interventions have been selected based on an interim analysis of outputs from the codesign workshops, which involved a high-level examination of the data from the Stage 1 activities to facilitate timely and actionable insights. Following the co-design workshops described in stage 1 sub-study 5, an internal peer review process was conducted among the study team, which included reflecting on the findings from the workshop and ultimately led to the refining, defining, and harmonizing of the proposed heat adaptation-mitigation interventions.

Table 2: Summary of main heat adaptation-mitigation intervention components which have been selected through the co-design process in Zimbabwe

	Behavioral	Built Env	Nature
Individual	
 
Personal Cooling Kits
 
Traditional Water-Cooling Systems
 
The Mother Heat Alert EWS
 
The Mass Media Radio Messaging
 
		
Household	
 
Partner Support and Family Support for Heat Stress Adaptation
 
	2) Cool Roofs	
Community	
 
Heat Champions
 
Watering hole hubs on adaptation & resilience for managing extreme heat risks - WARMER Model
 
Men's behaviour change model
 
Women's Self-Help Groups (SHGs
 
CHIEDZA - Chief-led Heat Intervention for Engagement, Dendemara-dialogue, & ZviAction
 
		6) Commu planting
Facility	
 
ANC Heat Health Talks
 
Waste Segregation
 
Hydration stations
 
The Water Buddie System
 
LED Heat Messaging Displays
 
Energy efficient refrigerants and refrigerators
 
	
 
7) Ceiling Installation and Repairs in Maternity and Postpartum Wards
 
8) Energy-Efficient Lighting
 
9) Solar Power Systems
 
10) Water Storage Tanks
 
	11) Facility  Planting
Policy			
TOTAL	16	5	2

Interventions at the facility level will be implemented at Mt Darwin Distict Hospital, Dotito and chitse health facilities. Household and community level interventions will be optimised in the catchment areas of these facilities. An estimated 50 households will be selected for continuous temperature monitoring in the dwellings where any built environment modifications will be implemented and monitiored.

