## 12.1.8. Intervention implementation procedures

This project employs action research cycles to implement and refine heat adaptation interventions across the catchment areas of Mt. Darwin District Hospital, Dotito, and Chitse rural health centers. These interventions will target individual, community, facility, and policy levels, creating a multi-tiered framework to address heat-related health risks. At the community level, interventions will include radio campaigns delivering heat-related health messages, traditional chief-led adaptation festivals to revive nature-revering practices, community woodland management to promote cooling and resource sustainability, and facility-level measures to enhance healthcare delivery under extreme heat conditions. Specific household-level interventions will be assessed first among a purposively selected group ranging from 10 up to about 50 pregnant women, thrir partner or their households depending on the nature of the intervention to ensure targeted, data-driven optimization. Selection criteria will include maternal age categories (16–24 years and >25 years), housing type, and geographic distribution across the communal areas of Chitse, Dotito, and Pfura within Mt. Darwin District.

Informed consent will be obtained using a two-step process. First, telephonic permission will be sought, followed by written consent from the household head, unless the pregnant woman herself is the head of the household. If the household head is unavailable, they may nominate a proxy to provide written consent. In cases where consent is withheld, the household and the pregnant woman will not be enrolled in the study. For consenting households, researchers will implement targeted interventions, including the installation of continuous temperature monitoring sensors, distribution of personal cooling kits (containing items such as portable fans and umbrellas), and modifications to the built environment, such as roof painting or thatching. Participants will also receive guidance on the optimal use of the built environment, including strategies for effective ventilation, shading, and scheduling work during cooler periods. Pregnant women in these households will also be exposed to heat early warning systems through messages delivered by trained community heat champions/village health workers, who will act as trusted messengers to promote behavioral changes and preparedness for heat events.

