
All information will be de-identified for analysis.

Data shared on public access platforms will be de-identified and adhere to the Wellcome Trust's policies for data accessibility and sharing [79].

Interviews will be audio-recorded and transcribed in full, with all identifying information removed from the transcripts, aside from gender, age, population group and facility name. Audio-recordings and transcripts will be stored in a secure folder and saved to the CeSHHAR SharePoint server with password-restricted access limited to the investigators and other study staff, and stored separately from other participant records such as informed consent forms that may identify individuals. After the study has concluded, audio-recordings will be destroyed in accordance with the time specifications mandated by the Medical Research Council of Zimbabwe, and the Wellcome Trust guidelines, whichever is longer.

There are several potential benefits to study participation, both for women and for their children. These include:

- Ability to track one's own heat exposure and activity
   Pregnant women participating in the study will be able to track their personal temperature exposure as well as their activity levels using the FitBit wearable device.
- 2) Acquisition of an activity tracker
  Upon study completion, women will be allowed to keep the FitBit device, at no cost to themselves. The device will be delinked from all study-related tracking mechanisms at the conclusion of the study. If the woman has a compatible smartphone, the study team will assist her with linking her wearable device to her smartphone.
- 3) Increased awareness of heat risks
  Through exposure to the study, participants may gain an increased awareness of the impact of heat exposure on the health of pregnant women and their infants. For pregnant women, this knowledge can empower them to take proactive measures to protect themselves and their babies from potential adverse effects. Moreover, at the community and facility level, the increased awareness may spark constructive dialogue

and the consideration of strategies to safeguard the well-being of pregnant and

postpartum women. This collective awareness will not only help to lay the groundwork for our entry into the second Stage of the project but may also lead to community-driven initiatives tailored to address the challenges posed by high temperatures.

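### The bias rule opens all study activities with heat-health background and exempts no cohort, so the pre-intervention cohort may receive some of the awareness component before its outcomes are measured

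*Protocol*

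**What the plan says.** Section 18.1.3 names one threat: participants may see heat as a nuisance and "under-report clinically-relevant symptoms". Its remedy is that "we will sensitise the communities and begin all activities by giving some background about heathealth risk". The sentence does not separate the pre-intervention from the post-intervention cohort. It does not say what the background contains or whether it comes before or after the measurements at a visit.

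The effectiveness comparison is set in Section 11: "Outcomes in the pre-intervention cohort of women will be compared with women in the post-intervention cohort". There is no concurrent control.

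Heat-health awareness is part of what is being tested. Section 6 describes the package as "encompassing behaviour change and awareness" among other elements. Table 2 in Section 12.1.2 lists "ANC Heat Health Talks" at facility level, with heat champions and radio messaging elsewhere. Section 12.1.8 adds "radio campaigns delivering heat-related health messages".

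The primary pilot-effectiveness outcome is urine specific gravity above 1.015 in labour, which Sections 11.1.5 and 18.1.2 say reflects hydration practices as well as heat exposure. Section 11.1.9 adds: "Follow-up visit interviewer-administered questionnaires will be shorter and focus on heat-related knowledge", together with heat and hydration behaviours.

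**The concern.** A pre-post study without a concurrent control depends on the pre cohort being free of the intervention until its last measurement. Table 1 in Section 11.1.10 protects this by dates: pre-cohort follow-up ends on 25 May 2025, and the intervention and co-design period starts on 1 June 2025. Section 18.1.3 works against that separation. Enrolment and antenatal follow-up visits of the pre cohort are study activities and they come before labour. The communities to be sensitised are the ones those women live in.

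Two things are at stake. First, if heat-risk information changes drinking or protective behaviour, the pre-cohort dehydration rate falls and the contrast shrinks. Second, if the background opens a visit, the knowledge answers that follow partly record what the woman has just been told, in either cohort.

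The remedy also does not suit the primary outcome. The rule targets self-reported symptoms. A refractometer reading gains nothing from it but can be moved by it through behaviour.

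**Working it through.** **Step 1. Is the pre cohort covered?** Section 18.1.3 does not name it. Coverage follows from the rule applying to all activities and to the communities, with no exemption. Section 8 states that this version describes Stage 2, and the rule directly follows the Stage 2 analysis section, so it cannot be set aside as text about the formative work.

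**Step 2. Does the content overlap the package?** Yes, with the awareness part: antenatal heat talks, radio messages, heat champions. It does not overlap the cooling, water-supply or building components.

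**Step 3. Is there a safeguard in the text?** Section 18.1.2 adjusts for multihazard factors and changes in climate exposures, not for the briefing. Section 28 does not list it as a limitation. Nothing standardises it or places it after measurement.

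**Step 4. Reproduce the planned power (Section 11.1.5).** Inputs:
- 400 women per cohort and 15% attrition: n = 400 × 0.85 = 340 per cohort.
- Pre-cohort rate p between 30% and 60%.
- Difference of 15%, read as percentage points. Read as a relative reduction, power would be only 26-66%, so the stated figure requires the absolute reading.
- Two-sided 5%. This is an assumption, because Section 11.1.5 states neither alpha nor sidedness.

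Formula: power = Φ[(d − 1.96 × SE0) / SE1], with d = p1 − p2, SE0 = √[2 × p̄(1 − p̄)/n], p̄ = (p1 + p2)/2, and SE1 = √{[p1(1 − p1) + p2(1 − p2)]/n}.

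At p = 60%: p1 = 0.60, p2 = 0.45, SE0 = √(2 × 0.249375/340) = 0.0383, SE1 = √(0.4875/340) = 0.0379, so power = Φ[(0.15 − 0.0751)/0.0379] = Φ(1.98) = 97.6%. At 45% it is 98.2% and at 30% it is 99.7%. The stated power above 95% reproduces, so the sample-size arithmetic is not at fault.

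**Step 5. Illustrate dilution.** Let f be the fraction of the 15-point effect that the briefing already produces in the pre cohort. The observed pre rate becomes p − 0.15f and the post rate stays at p − 0.15, so the contrast is 15 × (1 − f) points. This treats the briefed part as wholly redundant once the package is delivered. The documents give no value for f.

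| f (assumed) | Contrast, points | Power at p = 30% | p = 45% | p = 60% |
|---|---|---|---|---|
| 0 | 15 | 99.7% | 98.2% | 97.6% |
| 10% | 13.5 | 99.0% | 95.6% | 94.3% |
| 25% | 11.25 | 95.4% | 86.7% | 83.6% |
| 33% | 10 | 90.5% | 78.2% | 74.2% |

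Example, f = 1/3 and p = 60%: p1 = 0.55, p2 = 0.45, SE0 = √(2 × 0.25/340) = 0.0383, SE1 = √(0.495/340) = 0.0382, power = Φ[(0.10 − 0.0752)/0.0382] = Φ(0.65) = 74.2%.

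**The case against.** **The dose is small and unspecified.** The text promises only some background. It does not mention hydration or protective advice. Table 2 totals 23 components, many of them physical, such as hydration stations, water tanks, ceilings and cool roofs, and a briefing delivers none of these. This stands. A reader might infer that the briefing supplies a quarter, a third or more of the whole effect, but the documents give no basis for any fraction, and at 10% power is still 94-99%.

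**Both cohorts get the same briefing.** The contrast is then a coherent comparison of package plus briefing with briefing alone. If the effects simply added, the common part would cancel, and the contrast shrinks only as far as the briefing makes part of the package redundant. This also stands. It changes what is estimated, though: it is no longer the effect of the package against usual conditions.

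**Consent must explain the study's purpose anyway.** True, so some mention of heat is unavoidable in both cohorts. That argues for a short, neutral and identical wording, not for an open-ended instruction to give risk background.

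**Stronger readings that the documents do not support.** A reader might take Section 33, where "this knowledge can empower them to take proactive measures to protect themselves and their babies", as the protocol's own expectation that briefed pre-cohort women will change behaviour. That benefits list concerns wearers of activity trackers and speaks of preparing entry into the second stage, so it reads as formative-stage text, and its wording is conditional. A reader might also infer that the information is repeated at every later visit, or given minutes before each questionnaire. Section 18.1.3 fixes neither. Finally, heat knowledge and hydration practices are questionnaire items. Section 18.1.2 does not name them among the secondary outcomes.

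**The rule serves a purpose.** It tends to level awareness between cohorts for self-reported symptoms, and removing it has a price, given with the fix.

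**Conclusion.** The point holds as a cheap improvement to protocol wording. As written, Section 18.1.3 lets heat-health awareness content reach the pre-intervention cohort before its labour urine sample and its follow-up knowledge and hydration answers, and no other part of the protocol limits, times or accounts for it. For the refractometer-based outcome the likely direction is toward no effect. For self-reported symptoms the direction is uncertain, because heavier messaging in the post cohort can itself raise reporting.

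The size is unknown and may be modest. The power figures are illustrations that rest on assumed fractions, an assumed two-sided 5% test, the absolute reading of the 15% difference and full redundancy of the briefed part. They show that a small dilution costs little and that a third would take power to 74-91%. They do not show that such a dilution will occur. A later analysis plan cannot repair this, since exposure already given in the field cannot be removed by analysis.

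**What to change.** Replace the sentence in Section 18.1.3 with the following:

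- One neutral, scripted introduction, identical in both cohorts and limited to what consent requires, without heat-risk or protective messages.
- At each visit, the questionnaire and urine sample come before any heat-health information.
- Study-led heat-health education and community sensitisation in the catchments are held until pre-cohort outcome measurement ends. Routine care and advice from facility staff are not limited.
- Under-reporting is handled by the same neutral symptom checklist in both cohorts.
- If pre-cohort visits or sensitisation have already taken place, record what was said, to whom and when, and add it to Section 28 as a limitation.

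Cost: protocol and interviewer wording, staff training on the order of procedures, and later timing of community engagement, which should be agreed with the community and the ethics committee. Downside: some under-reporting of symptoms will remain, and it may differ between cohorts because only the post cohort receives the intervention messages. Self-reported symptoms therefore need cautious interpretation. The primary outcome is an instrument reading and is not affected by this.

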#### 19. DATA MANAGEMENT PLAN FOR ALL SUB-STUDIES

CeSHHAR Zimbabwe will be the data coordinating centre. This unit is headed by an experienced data manager. Data will be cleaned, entered, analysed and safely stored there and data maybe shared with Wits RHI in line with project data management guidelines.

Data management and security standards will be equivalent for routine programme data and data collection in pre and post surveys, though there will be significant differences in the way data are collected. For pre and post experimental serves, data will be collected using CAPI with assistance from a trained social scientist. Data validity checks will be built into the CAPI platform. In the field, data will be backed up daily into "cloud storage". Laptop computers on which any data may be stored will be kept in locked storage at all times. In the field, consent forms are kept in locked trunks and returned to the CESHHAR within 5 days of collating them. Field teams will download data into a password protected database accessible only to the Research manager and named PI, on a central computer. This will be backed up daily. The consent forms are kept separately from survey data. In Harare consent forms will be stored in a locked room at CeSHHAR offices.

For programme data, one hard-copy file linking participants' names with ID numbers, and contact/locator information will be maintained by the Research Manager and stored in a secure locked cabinet separate from participant data. Other hard-copy data will be stored separately in participant files and locked in a file cabinet located in a secure room accessible only to key study personnel. Participants will be asked to provide written informed consent for participation in the surveys and qualitative interviews. Specific data aspects are presented n subsections below:

#### **20. DATA MANAGEMENT**

Our data management plan includes the following key principles:

- Each participant will have a unique participant identification number. All hard copies of
  patient identifying data will be stored in a locked cabinet. Electronic versions of
  transcripts and original audio-recordings will be stored on a secure SharePoint site on
  our institutional server, which is secure and protected by two-level authentication.
- All of the data will be analysed electronically.
- Data will be fully anonymised or pseudonymised in reporting of the research findings,
   for example, when participant quotes are used.
- When storing a copy of the data on local machines is required (e.g., for qualitative analysis), the data will be password protected and de-identified.
- Access to data will be restricted to a limited number of study staff that have appropriate training to manage data.
- When sharing data with external transcribers, if required, they will not be sent by email but transferred safely using encryption or secure tools like Filesender or similar.
- The study will adhere to the Wellcome Trust regulations on data sharing.
- Many scientific journals now expect that datasets from the study being reported on are made accessible to readers, and some mandate this as a condition of publication.
   Access to the data collected in this study will be partly restricted - i.e., the dataset will be shared only upon written application to the study PI. More detailed aspects of data sharing are discussed in the section 5.3 of the protocol.
- Data will be shared between investigators at the two study sites.
- Data ownership will remain with the country teams in which the data was collected.

